1.4.3 Risk of Nasopharyngeal Swab

The primary risk of a nasopharyngeal swab is local discomfort. Rarely, there can be local bleeding from the nasal mucosa, which is controlled with local measures such as pressure or packing with gauze. Additionally the swab can cause coughing, gagging or infrequently vomiting.

1.4.4 Risk of Nasopharyngeal Aspirate

The primary risk of a nasopharyngeal aspirate is local discomfort. Rarely, this procedure can cause bleeding. Also, this procedure cause coughing, gagging, or vomiting.

1.4.5 Benefits

There may be no benefits to individual subjects for participation in this study. There may be earlier resolution of symptoms or fewer complications from SARI.

1.4.6 Alternatives

The alternative to participation in this study is routine standard of care (SOC). For suspected or confirmed severe influenza this will generally include an antiviral (likely oseltamivir or zanamivir based largely on availability and susceptibility).

2 STUDY OBJECTIVES

2.1 Primary Objective

The primary objective is to evaluate the effect of NTZ in addition to SOC as compared to PCB + SOC in the treatment of SARI as measured by the time to hospital discharge.

2.2 Secondary Objectives

1. Evaluate the clinical efficacy of NTZ + SOC vs. PCB + SOC with regards to:
 - Percent hospitalized at Study Day 3, 7, 14 and 28
 - Death by Study Day 28
 - Duration of clinical symptoms (defined in Section 7.3.1.2)
 - Duration of fever
 - Use of supplemental oxygen (or increase greater than baseline oxygen requirement)
 - Admission to ICU
 - Intubation/mechanical ventilation
 - Proportion of subjects who develop complications including pneumonia, respiratory failure requiring mechanical ventilation, acute respiratory distress syndrome (ARDS), sepsis, or bronchiolitis.
 - Time to resumption of normal activity
 - Antibiotic/antiviral use during hospitalization
 - Systemic corticosteroid use during hospitalization
 - Re-hospitalization within 28 days
2. Evaluate the virologic efficacy of NTZ + SOC vs. PCB + SOC with regards to:
 - Percent cessation of viral shedding at Study Day 3
3. Evaluate the safety and tolerability of NTZ assessed by:
 - Cumulative incidence and severity of AEs
 - Cumulative incidence of SAEs
 - Cumulative incidence of laboratory abnormalities on Study Days 3, 7 and 28

3 INVESTIGATIONAL PLAN

3.1 Research question

Does treatment with NTZ improve the outcome of subjects with SARI caused by respiratory viruses?

3.2 Hypothesis

NTZ improves the outcome of subjects with SARI caused by respiratory viruses, as measured by (duration of hospitalization, duration of symptoms, ICU requirements, O₂ requirements, use of antibiotics, etc).

3.3 Justification for the research

As respiratory viruses are major causes of ILI and SARI that can lead to severe outcomes including hospitalization and death, and the majority of these viruses have no available treatment, potential treatments of respiratory viruses causing SARI are needed.

3.4 Overview of Study Design

The study will be a multicenter, randomized, double-blind, placebo controlled trial to evaluate the efficacy of NTZ+ SOC compared to PCB + SOC in treating acute viral respiratory infections in adults and children \geq 12 months old with SARI. The study will be conducted in up to 8 sites within Mexico, at sites that are part of the LaRed network. Subjects will be selected according to the inclusion and exclusion criteria listed below (Sections 4.3 and 4.4). The study is designed to enroll a total of 290 subjects who will be randomized in a 1:1 ratio. Enrollment will continue until 290 subjects are randomized, or March 2017, whichever comes first.

Prior to screening for inclusion in the study, informed consent (and assent for pediatric subjects as applicable) will be obtained. After completion of informed consent, screening for the study will occur. This involves review of the subjects' symptoms, medical conditions, physical exam, and pregnancy test for females able to become pregnant. All patients will initially be hospitalized. If the subject qualifies for the study, baseline assessments will occur including baseline vitals, safety labs, and nasopharyngeal swab or aspirate for PCR. Subjects will be randomized to a treatment kit and will begin treatment immediately. They will receive instruction on completion of their diaries, concomitant medications, and attending follow-up visits. Subjects will be followed on Study Days 3, 7, 14, and 28. The subject will be discharged from the hospital when clinically indicated as determined by the treating physician – follow-up visits may occur as inpatients or as outpatients.

On Study Days 3 (+/- 1) and 7 (+/- 1) a clinical assessment will be performed, diary cards collected, and safety labs will be obtained. Subjects that are hospitalized on Day 14 will have an in person visit. For subjects that are no longer hospitalized, the Day 14 visit may occur in person or by telephone. This visit is primarily for the collection of Day 7-14 diary card information. Study Day 28 will mark the end of study where subjects return for final clinical assessment, safety labs, and convalescent serologies.

Subjects that are still hospitalized after Study Day 28 will continue to be followed through the date of discharge.

3.5 Definitions for the Purpose of this Study

Enrolled

For the purpose of collecting data and samples and reporting AEs, a subject will be considered enrolled beginning from the time the informed consent form is signed until the subject is considered “screen failure”, “discontinued”, or “completed”.

Randomized

Subjects are considered randomized when they meet all of the following criteria:

- Confirmation that the inclusion and exclusion criteria are met
- Consent is given and signed by the subject for the study
- Randomization number is assigned

Screen Failures

Subjects are considered screen failures when they meet 1 of the following criteria after signing consent:

- Screening tests reveal that the subject is ineligible
- Subject withdraws consent before being randomized

Discontinued

Subjects are considered discontinued when they meet 1 or more of the following criteria:

- Subject withdraws consent after being randomized (see Section 4.5)
- Subject is withdrawn after enrollment by investigator (see Section 4.7) including lost to follow-up

Completed

Subjects are considered completed when they are followed through Study Day 28 and complete the final study follow-up visit (Study Day 28) or die prior to this study visit.

3.6 Study Endpoints

3.6.1 Primary Endpoint

Duration of hospitalization (days and hours)

3.6.2 Secondary Endpoints

Clinical Endpoints:

- Hospitalization on Study Days 3, 7, 14, and 28
- Date and time of hospital discharge
- Date of death, if applicable
- Clinical symptoms (measured daily through Study Day 14 and then again on Study Day 28)
- Temperature (measured daily through Study Day 14 and then again on Study Day 28)
- Oxygen use
- Date of admission to ICU and discharge from ICU, if applicable
- Date of intubation/extubation, if applicable
- Presence of complications during study (pneumonia, respiratory failure requiring mechanical ventilation, ARDS, sepsis, or bronchiolitis)

- Global assessment (measured daily through Study Day 14 and then again on Study Day 28) (defined in Section 7.3.1.3)
- Antibiotic/antiviral use during hospitalization (number and duration)
- Re-hospitalization within 28 days
- Use of systemic corticosteroids

Virologic Endpoints:

- Presence of virus on nasopharyngeal (NP) swab (or aspirate) on Study Day 3 (same virus as Day 0)

Safety Endpoints:

- AEs
- SAEs
- Chemistry and hematologic laboratory assessments on Study Days 3, 7 and 28

4 STUDY POPULATION**4.1 Rationale for Research Subject Selection**

The inclusion criteria define those subjects with SARI. In an ongoing LaRed study, similar ILI criteria have been successful in identifying a population whose respiratory illness is caused by a virus 70% of the time.

4.1.1 Justification for the Inclusion of Children \geq 12 Months Old

In Mexico, nitazoxanide is licensed by COFEPRIS from 2 years old indicated for the treatment of diarrhea caused by *Giardia lamblia* and by *Cryptosporidium parvum*. In the US Nitazoxanide is approved by FDA for the management of diarrhea caused by *G. lamblia* or *C. parvum* in pediatric Subjects 1 year of age and older. Nitazoxanide pediatric dosage recommendations are summarized in Table 3.

Table 3: Pediatric Nitazoxanide Dosage Recommendations

Disease	Maximum dosage
Diarrhea caused by G. lamblia or C. parvum	
• 1-3 years of age: 100 mg (or 5 mL as oral suspension) every 12 hours (with food) for 3 days• 4-11 years of age: 200 mg (or 10 mL as oral suspension) every 12 hours (with food) for 3 days• \geq 12 years of age: 500 mg (or 25 mL as oral suspension) every 12 hours (with food) for 3 days

* Tablets are only approved for use in children 12 years of age and older.¹⁹

However, there is evidence in papers of nitazoxanide administered in children less than 2 years old. One study was conducted to assess the activity of nitazoxanide in hospitalized pediatrics Subjects with severe gastroenteritis due to Rotavirus. In that trial drug has been used in children from 5 months old. The blinded study medication was administrated as: children 12-47 months of age 5mL (100 mg) twice a day for 3 days, and 7.5 mg/kg twice a day in subjects younger than 12 months. They found no adverse experiences associated with the use of nitazoxanide. There

were no significant adverse events, only two events (one case of mild otitis media and one case of mild bronchitis) both these subjects were in the placebo treatment group.²⁰

In another large study in Egypt nitazoxanide there were included 546 subjects. They took medication with food at 12-hour intervals over 3 days; those older than 12 years received 500 mg of nitazoxanide, children aged 4 to 11 years received 200 mg of drug, and children aged 1 to 3 years received 5 mL of a 100 mg per 5 mL suspension. Their results indicate that nitazoxanide is safe and effective for treating intestinal protozoan and helminthic infections with eradication rates of 81% for intestinal amebiasis, 94% for giardiasis, and 77% for balantidiasis.²¹

4.1.2 Justification for the Exclusion of Pregnant Women and Children < 6 Months Old

Given the lack of known efficacy of the combination and the potential toxicities including teratogenicity, pregnant women are excluded from this study.

NTZ is licensed in the US and Mexico for adults and children (1 year of age and older in the US and 2 years and older in Mexico) for gastrointestinal parasitic diseases (*Giardia lamblia* or *Cryptosporidium parvum*). Given the clinical impact of respiratory viruses and SARI in children (as previously described), children (greater than or equal to 12 months) are eligible for inclusion in this study. The use in children under 2 years of age in Mexico, and the use for respiratory infections are investigational.

As the safety of nitazoxanide in children < 12 months of age has not been established, these children will be excluded.

4.2 Recruitment

Subjects will be recruited through the hospital sites in Mexico that comprise LaRed. Information about this study will be disseminated to health care providers in these settings. Subjects that have been recently hospitalized with ILI, or that are in the emergency department or clinic that are going to be hospitalized with ILI will be evaluated for potential participation in this study. Additionally, direct-to-subject recruitment (using posters and/or other informational items) may occur in these hospital settings.

Any direct-to-subject recruitment documents/materials will be submitted to the reviewing Institutional Review Board (IRB)/Independent Ethics Committee (IEC) for approval. Any flyers and advertisements that will be viewed directly by potential study subjects will be submitted to the site IRB/IEC for approval.

Informational items about the study distributed to the health care staff only, including but not limited to the manual of procedures are not required to be reviewed by the IRB/IEC.

4.3 Inclusion Criteria for Enrollment

1. Signed informed consent prior to performance or initiation of any study procedures.
2. Age \geq 12 months of age (no upper age limit).
3. One of the following constitutional signs or symptoms within 7 days of screening:
 - Temperature of $\geq 38^{\circ}$ C

- Temperature \leq or 36° C
- Myalgia
- Headache
- Malaise
- Irritability (children < 5 years of age only)
- Decreased appetite (children < 5 years of age only)

4. One of the following lower respiratory sign/symptom within 7 days of screening:

- Cough
- Hypoxia ($\text{SaO}_2 < 95\%$)
- Tachypnea (age adjusted, see section 7.3.4)
- Dyspnea
- Nasal flaring (children < 2 only)
- Chest retractions (children < 2 only)

5. Hospitalization for ILI (decision for hospitalization will be up to the individual treating clinician), with anticipated hospitalization for more than 24 hours.

6. One of the following to avoid pregnancy:

- Females who are able to become pregnant (i.e., are not postmenopausal, have not undergone surgical sterilization, and are sexually active with men) must agree to use at least 1 effective form of contraception from the date of informed consent through Day 28 of study. For hospitalized subjects, this can begin after hospital discharge.
- Males who have not undergone surgical sterilization and are sexually active with women must agree to use condoms or have a partner use at least 1 effective form of contraception through Day 28 of study. For hospitalized subjects, this can begin after hospital discharge.

4.4 Exclusion Criteria

1. Women who are pregnant or breast-feeding.
2. Clinical suspicion that etiology of illness is primarily bacterial in origin.
3. Prior treatment with antivirals (e.g. oseltamivir) for the current illness for more than 24 hours.
4. Subjects unable to take enteral medications (adults must tolerate tablets by mouth as they cannot be crushed, children must be able to swallow pediatric suspension or receive drug by nasogastric tube).
5. Prior treatment with any investigational drug therapy within 30 days prior to screening.
6. Known sensitivity to NTZ or any of the excipients comprising the NTZ tablets.
7. Prior NTZ use within 1 week.
8. Self-reported history of impaired renal function (no blood or urine kidney function laboratory testing will be done prior to enrollment, but intent is to exclude disease severe enough to cause estimated $\text{CrCl} < 30 \text{ mL/min}$).
9. Self-reported history of liver disease (no blood laboratory testing will be done prior to enrollment, but intent is to exclude disease severe enough to cause cirrhosis or total bilirubin $> 1.5 \times \text{ULN}$, $\text{AST}/\text{ALT} > 3 \times \text{ULN}$, based on labs obtained previously for clinical diagnosis).

10. Presence of any pre-existing medical condition not listed above that, in the opinion of the investigator, would place the subject at an unreasonably increased risk through participation in this study.
11. Subjects who, in the judgment of the investigator, will be unlikely to comply with the requirements of this protocol.
12. The onset of respiratory symptoms occurs after hospitalization (to exclude nosocomial infections).
13. Hospitalized for any reason for greater than 60 hours prior to enrollment.
14. Participants previously enrolled in this study.
15. Known chronic respiratory infection (e.g., tuberculosis, atypical mycobacterial infections).

4.5 Subject Withdrawal

Subjects (or their parents or legal surrogates if subjects become unable to make informed decisions) can terminate study participation at any time without prejudice. If a subject terminates participation before completing the study, the reason for this decision will be recorded in the case report form (CRF).

Subjects who indicate interest in withdrawing from the study should also be asked permission to be contacted at Study Day 28 by telephone for vital status (any AEs that occurred during the study). This is not considered full withdrawal of consent, and the agreement for limited follow-up should be noted in the medical record.

Subjects who fully withdraw consent will not be contacted further.

Subjects who withdraw from the study will not be replaced.

4.6 Discontinuation of Study Medication

Subjects will discontinue study medication for any of the following reasons:

- Laboratory results from baseline or subsequent visits that show any of the following:
 - Estimated CrCl <30 mL/min
 - Total bilirubin >2×ULN
 - AST/ALT >3×ULN
- The subject becomes unable to take oral medications (study drug cannot be given by nasogastric tube without unblinding)
- Clinically significant grade 3 or 4 AEs (including safety laboratory results) that in the judgment of the site investigator are causally related to study medication
- Any other AE or clinically significant laboratory result for which the investigator believes that continuation of the study medication would be detrimental to the subject
- Positive pregnancy test

Subjects who discontinue study drug should still be treated with standard care treatments (Section 5.6).

The reason for discontinuation of the study drug is to be recorded on the CRF. All subjects who discontinue study drug will be encouraged to comply with the study visit schedule including

clinical and virologic assessment through Day 28.

4.7 Discontinuation of Subject by Investigator

The investigator has the right to withdraw subjects from the study. Subjects may be withdrawn from the study for any of the following reasons:

- The subject is lost to follow-up
- The subject experiences an AE and the investigator believes that continuation in the study would be detrimental to the subject (in contrast to discontinuing the study medication and continuing follow-up as discussed in Section 4.6)

The reason for withdrawal from the study is to be recorded on the CRF. If a non-serious AE is unresolved at the time of discontinuation, efforts should be made to follow-up until the event resolves or stabilizes, the subject is lost to follow-up, or there is some other resolution of the event. The investigator is to make every attempt to follow all SAEs to resolution.

Subjects who miss a study visit should be contacted to reschedule. If subjects cannot be contacted immediately, periodic attempts should continue until study completion (Study Day 28). Lost to follow-up is defined as unsuccessful contact after at least 2 documented telephone calls.

Any subject withdrawn from the study will not be replaced.

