9.1 General Considerations

This is a double-blind, randomized, placebo, controlled trial in patients with hospitalized influenza-like-illness to evaluate the efficacy of NTZ compared to placebo on the time to hospital discharge. The primary analysis will use the Shaw-Fay formulation of the 2 sample Mann-Whitney-Wilcoxon rank-sum statistic. The primary endpoint will be time to hospital discharge, censored at 28 days. Patients who withdraw consent will be counted as being censored at the time of withdrawal. Patients who die by Day 28 will receive the worst ranks, (i.e., worse than any patients who remain hospitalized). Furthermore, patients who die earlier will receive worse ranks than those who die later. Patients who withdraw consent prior to day 28 are thus censored for death and discharge at the time of withdrawal. Such censoring is addressed by the method of Shaw and Fay (2013). A permutation method will be used to determine statistical significance. The primary analysis will follow the intent-to-treat principle where all randomized patients will be used in the analysis. The primary analysis will use a two-sided alpha level of .05.

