9.2 Sample Size and Power Calculations

Sample size calculations are based on the primary endpoint only (i.e. Duration of hospitalization). Secondary endpoints may or may not be adequately powered with the chosen sample size.

When there is no censoring or deaths, power for the two-sample Mann-Whitney-Wilcoxon rank-sum test can be approximated assuming that days of hospitalization follows a log normal distribution. The parameters used in the calculation were from the observed distribution of days to hospital discharge for hospitalized subjects who enrolled in the ILI002 observational study. We obtained data on patients who survived with hospitalization less than 28 days. The data were truncated at 28 days to avoid the influence of aberrant values on the estimates. This eliminated about 4% of the data. The mean and variance of the days in the hospital were 7.7 and 33.2. We assumed that the effect of treatment would be to reduce the number of days in the hospital by Delta but that there would be no effect of treatment on the variance of the number of days in the hospital. Thus for the treatment group the mean and variance are given by 7.7-Delta and 33.2, where Delta is varied. We next assume that the distribution of days to hospital discharge followed a log-normal distribution in each group, which is equivalent to assuming that the log(Days) follows a normal distribution, where Days is the number of days until hospital discharge. A log-normal distribution is specified by its moments $E\{\log(Days)\} = m$ and $\text{var}(\log(Days))=v$. These moments are related to the mean, $E(D)$, and variance, $V(D)$, of the number of days (D) in the hospital by the formulas.

$$m = \log\{E(D)\} - v/2$$

$$v = \log\{1 + V(D)/[E(D) \times E(D)]\}.$$

For simplicity, we determine the sample size for different assumptions of treatment effects of nitazoxanide, using a two sample t-test with unequal variances using Satterthwaite's method (Table 8). This method requires the mean and variance of log (Days) for the 2 groups, which are obtained by solving the above equations separately for the placebo and treatment groups. Calculations were performed using Nquery 7.0.

Table 9: The total sample size required to achieve different powers under different assumptions about the benefit of nitazoxanide (Delta) using a two-sided .05 level test

Moments for the log days in hospital						
	Placebo Group		Treatment Group			
Delta ^a	m ₀₀	Sqrt(v ₀)	m ₀	Sqrt(v ₀)	Power	N ^b

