1.50 Days	1.83	.66	1.52	.78	80%	174
1.50 Days			1.52	.78	90%	232
1.25 Days	1.83	.66	1.58	.76	80%	258
1.25 Days			1.58	.76	90%	344
1.00 Day	1.83	.66	1.64	.74	80%	430
1.00 Day			1.64	.74	90%	576

^a Delta is the assumed reduction in the mean number of days in the hospital under treatment compared to placebo.

^b N is the total sample size.

We see that with about 258 patients total the study is 80% powered to detect a 1.25 day improvement in the time to hospital discharge. This difference is similar to our assumptions. To allow for up to 10% dropouts we will recruit 290 patients. If the difference was 1.5 days, the study would have 90% power to detect the difference in the treatment arms.

While a 1.25 day improvement is clinically meaningful and easily interpretable for a population with a mean hospital stay of 7.7 days, it is also a reasonable estimate of the effect of NTZ we might see. The NTZ IB describes a Phase 2b-3 study in adults and adolescents with acute uncomplicated ILI. In all subjects, the mean time to resolution of symptoms was 95 hours in the NTZ group compared to 108 hours in the placebo group, thus there is about a 12% reduction in the time to resolution (12% = (108 hr - 95 hr)/108 hr x 100%). Our hoped for treatment effect of a 1.25 day reduction in hospital duration is a 16% reduction in the time to hospital discharge (16% = (1 day/7.7 day x 100%)).

Kaplan Meier curves of time to hospitalization discharge over 28 days will be used to compare the 2 groups. In these curves, deaths will be counted as being in the hospital at day 28. The between group difference in median time to discharge will be used to estimate the treatment effect and will be reported along with a 95% two-sided confidence interval.

Important additional analyses will be to repeat the primary analysis for those who are influenza positive. Other subgroups include age (<12 years of age, \geq 12 years of age) and pathogen type.

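### Withdrawal by the investigator for an adverse event can end collection of the primary outcome, although the hospital chart still holds it

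*Protocol*

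**What the plan says.** **Leaving the study.** Protocol 4.6 covers stopping study drug, and there "All subjects who discontinue study drug will be encouraged to comply with the study visit schedule" through Day 28. Section 4.7 adds a different step, withdrawal from the study itself. One reason is loss to follow-up. The other is that "The subject experiences an AE and the investigator believes that continuation in the study would be detrimental to the subject", which 4.7 expressly distinguishes from stopping drug while follow-up goes on.

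**What ends then.** Section 3.5 defines, for data collection, a period that closes when a subject is a screen failure, discontinued or completed. Its definition of discontinued includes withdrawal under 4.7 and loss to follow-up.

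**What is kept.** Section 4.5 asks for a Day 28 vital-status call, but only for subjects who themselves want to withdraw. Section 4.7 asks for serious events to be pursued to resolution and for efforts to follow non-serious events until they resolve or stabilise. Section 6.2.8 takes discharge and death dates from the medical chart.

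**Loss.** In 4.7, "Lost to follow-up is defined as unsuccessful contact after at least 2 documented telephone calls", while after a missed visit "periodic attempts should continue until study completion (Study Day 28").

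**Analysis.** Protocol 9.1 says "Patients who withdraw consent will be counted as being censored at the time of withdrawal" and gives deaths by Day 28 the worst ranks. SAP Appendix 1 sends subjects lost to follow-up to the Shaw-Fay ranks for missing data, and explains loss as withdrawal of consent. Neither names withdrawal by the investigator.

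**The concern.** The primary endpoint needs two facts per subject: when the subject left hospital, and whether the subject was alive at Day 28. Neither needs a study procedure. The discharge date is in the chart and vital status takes a call.

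A subject taken off study for an adverse event while still an inpatient is plausibly more likely than others to stay long or die. A censored-data rank is fair only if censoring is unrelated to prognosis, and here it may well be related. If such withdrawals were more frequent on nitazoxanide, some of its worst outcomes would be replaced by middling ranks. If they were more frequent on placebo, the bias would run the other way.

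The 10% dropout allowance protects power against lost numbers. It does nothing about selective loss.

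**Working it through.** **1. The plan's own figure.** Inputs from Protocol 9.1 and 9.2: "The primary analysis will use a two-sided alpha level of .05"; "The mean and variance of the days in the hospital were 7.7 and 33.2"; "with about 258 patients total the study is 80% powered to detect a 1.25 day improvement". The sample-size table prints log-scale means and SDs of 1.83 and 0.66 (placebo) and 1.58 and 0.76 (treatment).

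- Normal approximation, per arm: (0.66² + 0.76²) × (1.960 + 0.842)² / 0.25² = 1.0132 × 7.85 / 0.0625 ≈ 127.2, so 128 per arm, 256 in all. The unequal-variance t-test with Satterthwaite degrees of freedom gives 258, as stated. (Unrounded moments, 1.819/0.667 and 1.571/0.766, give 266.)
- Dropout: 258 / 0.9 = 287, against 290 planned.
- Power with unrounded moments: 83.5% with all 290, about 79% if 10% carry no information. Full outcome collection would thus recover at most about 4 points of power. The larger question is bias.
- Design effect as a win probability: Φ(0.25 / √1.0132) = Φ(0.248) = 0.598, or 9.8 points above 0.5.

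**2. The path to a missing outcome.** A subject withdrawn in hospital under 4.7 is discontinued under 3.5. The 6.2.8 form falls due only after the later hospital discharge, outside the collection period. The 4.5 call does not apply. The safety follow-up in 4.7 may reveal a death or long stay, but neither document says that this feeds the primary ranks.

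**3. Size per subject.** As a single-event shortcut, not the exact bivariate Shaw-Fay score, a subject censored at quantile F has expected rank (1 + F)/2. With the placebo log-normal:

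- Day 2: F = Φ((ln 2 − 1.819)/0.667) = 0.05, expected rank 0.52.
- Day 5: F = Φ((ln 5 − 1.819)/0.667) = 0.38, expected rank 0.69.

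The true rank is an assumption. At the 97th percentile (death or a very long stay) the shift is 0.97 − 0.69 = 0.28 to 0.97 − 0.52 = 0.45. For a 14-day stay, Φ((ln 14 − 1.819)/0.667) = 0.89, and the shift is 0.20 to 0.37. If the subject's course is like that of others still in hospital, the shift is nil. Multiplied by the share of one arm affected, each 1% of the nitazoxanide arm (1.45 of 145 subjects) moves the win probability by 0 to 0.45 points.

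**4. Error rate.** Null simulation with 290 subjects and 4,000 runs. Assumptions not in the documents: 5% mortality in each arm; poor course means death or a stay over 14 days; withdrawal at 30–80% of the time to event; pairwise Gehan-type scores in place of exact Shaw-Fay ranks; a normal approximation for the permutation test. Nominal one-sided error is 0.025, with simulation standard error √(0.025 × 0.975 / 4000) ≈ 0.0025.

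| Poor-course subjects withdrawn | Share of all subjects | Error favouring nitazoxanide |
|---|---|---|
| None | 0 | 0.023 |
| 30%, both arms | 4.6% | 0.025 |
| 30%, nitazoxanide only | 2.3% | 0.032 |
| 50%, nitazoxanide only | 3.9% | 0.050 |
| 100%, nitazoxanide only | 7.7% | 0.076 |

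At 10% mortality, withdrawing 50% on nitazoxanide only gave 0.058.

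**5. Telephone loss.** Losing 10% of subjects after a recorded discharge left the error at 0.022.

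**The case against.** **Safeguards exist.** Section 4.7 itself requires serious events to be pursued to resolution, and section 8.1 counts death and prolonged hospitalisation as serious. This stands as mitigation, not as a cure: it is safety reporting, with no stated route into the primary ranks.

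**The SAP plans for missing outcomes.** In SAP section 11, one analysis censors missing placebo subjects and counts missing nitazoxanide subjects as events at Day 28; another counts both so. The first is aimed at bias favouring nitazoxanide. But it is not said whether an event is a discharge or a death. A discharge at Day 28 would rank better than a subject still in hospital, and a death at Day 28 would be the mildest of the deaths. Neither analysis recovers a date already in the chart.

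**Imbalance may be slight.** The trial is double-blind. Section 1.4.1 reports that under 1% stopped therapy for an adverse event in earlier studies, with common events similar to placebo. Those were not this population, and leaving a study is a further step than stopping drug. Still, it is the only rate the documents give, and it points to a small effect.

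**Stronger readings that the text does not support.**

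- A reader might infer that two failed calls close a subject out. But 4.7 says at least two calls and continued attempts to Day 28. The two sentences need reconciling, no more. The rule mainly touches discharged subjects, whose discharge time is recorded; only a later death would be missed, although SAP Appendix 1 does rank such a death worse than any survivor.
- A reader might infer that censored subjects go unranked. SAP Appendix 1 gives them a rank; the question is whether it is fair.
- A reader might put the bias at about 1 point of the 9.8. That needs 3% of the nitazoxanide arm withdrawn with no offset on placebo, and all of them truly near the 97th percentile.
- A reader might want the adverse-event provision deleted. It also lets an investigator stop blood draws and swabs, and the gap can be closed without removing it.

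**Conclusion.** The gap is real but narrow. As written, 4.7 with 3.5 allows outcome collection to stop for a subject withdrawn by the investigator for an adverse event, with no duty to obtain the discharge date or Day 28 vital status. The handling of such subjects in the primary analysis is also unstated; that they are censored is an inference from how the SAP treats loss to follow-up.

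The direction and size of any bias are unknown, because the documents give no rate of such withdrawals. It is small if they are rare or balanced. With 1% of the nitazoxanide arm affected and none on placebo, a true course between a 14-day stay and death gives 0.20 to 0.45 points of the 9.8-point design effect. Clear inflation of the error rate needed several percent of one arm, selected for poor course. The telephone-loss wording is a drafting point with little effect on the primary result. This merits a short amendment because the missing data are avoidable, not because the trial's conclusion is in evident danger.

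**What to change.** 1. In Protocol 4.7 and 3.5, keep the adverse-event provision, but state that withdrawal by the investigator ends study drug and study procedures, not outcome collection.
2. For every randomised subject who has not withdrawn consent, complete the 6.2.8 discharge form from the chart and obtain Day 28 vital status. Confirm that the consent form covers this.
3. Reconcile the two sentences in 4.7 so that loss to follow-up is declared only after attempts have continued to Day 28.
4. Name investigator withdrawals in Protocol 9.1 and SAP Appendix 1, with the rule for ranking them.
5. Add to SAP section 11 a sensitivity analysis giving any remaining withdrawn or lost subjects the death rank, and say what an event at Day 28 means in the two existing analyses.

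The cost is a short amendment and a few chart checks and calls by existing staff. No rule on dosing or on stopping study drug changes.
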